#### **7.2.2.10 Visit 4 (Visit 1 plus 24 weeks [ $\pm$ 3 days] or Early Termination)**

Subjects will be instructed to arrive having fasted from the night before this visit and having taken their morning dose of the study drug with time taken noted.

- Assessment for any AE/SAE will be completed
- Medical history will be taken
- Routine physical examination will be performed
- ECG test will be performed
- Study drug will be discontinued
- Sudorimetry
  - Sudoscan
- Autonomic Function Tests
  - Heart Rate Variability (HRV)
  -
- Blood will be taken for the determination of HbA1c, lipids, clinical chemistry variables, hematology, c-peptide, inflammatory markers and oxidative/nitrosative stress (see study schedule).
- Total amount of blood drawn at this visit will be approximately 55-60 ml.
- Urine will be obtained for measurement of microalbumin

- An OGTT will be administered and OGTT glucose and insulin levels will be obtained at 0, 30, 60, 90 and 120 minutes post-glucose challenge.
- Skin Blood Flow (SkBF)
  - Continuous Laser Doppler
- Quantitative Sensory Tests (QST)

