## **7.3 STATISTICAL METHODS**

Statistical analyses will be conducted on between group (bromocriptine-QR vs. placebo) differences in change from baseline of all primary and secondary endpoints. The treatment effects on all of the primary and secondary outcomes will also be assessed as a function of the duration of diabetes and other baseline demographics such as HbA1c, concomitant medications and metabolic status. Mean differences of glycemic control, various derivative autonomic function values, and inflammatory marker levels will be compared first using standard Analysis of Variance (ANOVA), with diagnostic group entered as the predictor variable. Within-group analysis for change in primary and secondary endpoints after 12 weeks of treatment will be done using repeated measures MANOVA (multivariate analysis of variance). For glycemic control analysis patients will be stratified according to post-prandial insulin response. If data are not normally distributed, the Wilcoxon signed-rank (within group) or Mann Whitney (between group) tests may be employed or Fisher's exact test in case of small sample sizes. The level of significance will be set at  $p < 0.05$ . Relationships and/or trends between the effect of Cycloset on neurovascular function and diabetic neuropathy will be determined with Spearman's rank correlation.

A statistical analysis plan (SAP), providing details of the analyses and presentation structure of the results, will be developed and finalized before the database is locked.

A local laboratory will be utilized for collection and analysis of the laboratory tests associated with efficacy, and safety. Standardized guidelines for preparation, collection, and centralized analysis of blood specimens will provide uniformity of the data and will avoid potential inter-laboratory variability due to inconsistent methodology.

The analyses of plasma markers of inflammation, oxidative/nitrosative stress, neuroendocrine factors, and the adiponectin/leptin ratio will be conducted at VeroScience (Tiverton, RI).

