bromocriptine-QR's impact to reduce elevated RHR was an independent predictor of its effect to reduce HbA1c among subjects with poor glycemic control (baseline HbA1c ≥ 7.5)⁴¹. The rationale for the categorical stratification of ≥ 70 or < 70 BPM for the analysis of the data from this current study is therefore based on the above considerations. A subset analysis will also be conducted in subjects with baseline RHR ≥ 80 BPM. We hypothesize that the treatment effect on SNS will be expressed in the RHR ≥ 70 BPM group.

Secondary Endpoints:

1) Measures of insulin resistance and glycemic control

Given the mechanism of action of Cycloset to improve postprandial insulin sensitivity, the main endpoint that will be evaluated is the effect of study drug treatment on postprandial glycemic control based on the OGTT plasma glucose and insulin data obtained at baseline and week 24. Between treatment group differences in change from baseline to week 24 for the area under the curve as well as levels at different time points of OGTT plasma glucose and insulin levels will be analyzed. Matsuda index of insulin sensitivity calculated using the OGTT glucose and insulin levels and HOMA-IR calculated from fasting glucose and insulin levels will also be analyzed as measures of insulin sensitivity/resistance.

All subjects completing 24-weeks of study drug treatment with data for baseline and week 24 OGTT will be included in the analyses of glycemic endpoints. The analyses will be done in the entire cohort of subjects with and without stratification by baseline HbA1c level of < 7.0 and ≥ 7.0 (i.e. suboptimal glycemic control).

Given that as a postprandial insulin sensitizer, the presence of adequate postprandial insulin levels is an important determinant of the postprandial glucose lowering efficacy, further subset analyses will be conducted to assess the above endpoints in subjects with OGTT insulin at T60 mins ≥ 50 $\mu\text{U/ml}$ and also in the subset on an insulin secretory agent (+/- TZD). An analysis stratified by duration of diabetes (≤ 4 years or > 4 years) may also be conducted depending on sample size.

2) Measures of inflammation, oxidative/nitrosative stress and plasma neuroendocrine factors

The following plasma factors will be evaluated: cortisol, aldosterone, norepinephrine, normetanephrine, adiponectin, leptin, IL6, TNF α , PAI1, SOD, TBARS, ADMA, nitrotyrosine and other appropriate factors of increased systemic inflammation and reactive oxygen species.

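### The SAP's main glycaemic endpoint is a domain with no lead variable and no multiplicity rule, which allows up to 70 between-arm tests (98 with optional strata) at p < 0.05

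*SAP*

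**What the plan says.** Under Secondary Endpoints, item 1, the SAP declares that "the main endpoint that will be evaluated is the effect of study drug treatment on postprandial glycemic control". It then plans between-arm comparisons of the week-24 change in "the area under the curve as well as levels at different time points of OGTT plasma glucose and insulin levels". Two indices are added: Matsuda, from the OGTT values, and HOMA-IR, from the fasting values.

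The SAP does not list the time points. Protocol 7.2.2.1, 7.2.2.7 and 7.2.2.10 give the sampling: "OGTT glucose and insulin levels will be obtained at 0, 30, 60, 90 and 120 minutes post-glucose challenge".

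The analyses are to be run in the entire cohort (24-week completers with both OGTTs) "with and without stratification by baseline HbA1c level of < 7.0 and ≥ 7.0". Further subsets are subjects with 60-minute OGTT insulin of at least 50 µU/ml and subjects on an insulin secretory agent. A split by diabetes duration is optional and depends on sample size.

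The SAP's Statistical Methods apply an independent-samples t-test to every endpoint, with a non-parametric fallback, and give no alpha. The level comes from the protocol (7.3, repeated in 9.7): "The level of significance will be set at" p < 0.05. Neither document gives a lead variable, a testing order, an adjustment or an exploratory label for this family. Protocol 7.3 also specifies that the glycaemic analysis is stratified by post-prandial insulin response.

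**The concern.** Calling something the main endpoint suggests that one result will answer the glycaemic question. Here the label covers a domain measured by many variables, each tested in several overlapping groups at the same unadjusted level. Nothing in the plan says which result is the answer. A glycaemic benefit could be reported from whichever time point or subset falls below 0.05, and the objective has no test with a 5% error rate.

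This is a co-secondary objective. What is at stake is how far a glycaemic finding can be relied on, not the error rate of the primary autonomic endpoint.

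**Working it through.** The documents give no number of tests and no family-wise error rate for these endpoints, so there is no plan figure to reproduce. The stated power above 0.80 with 80 participants (Protocol 9.7) concerns a 10% change in an unnamed endpoint with no standard deviation, and does not bear on this count.

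**Step 1: variables.** There are two analytes (SAP), each with one AUC and k time-point levels, plus Matsuda and HOMA-IR. Variables = 2 × (k + 1) + 2. With all five sampled times, the OGTT variables number 2 × (5 + 1) = 12, and the total is 14.

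**Step 2: analysis sets.** Five are firm: entire cohort, HbA1c < 7.0, HbA1c ≥ 7.0, 60-minute insulin ≥ 50 µU/ml, and secretory-agent users. Two duration strata are optional, making seven.

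**Step 3: expected number significant with no drug effect.** Expected = variables × sets × 0.05. This mean does not depend on the correlation between tests.

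| Time points used | Variables | Five sets: tests, expected | Seven sets: tests, expected |
|---|---|---|---|
| 5 | 14 | 70, 3.5 | 98, 4.9 |
| 4 (fasting sample left out) | 12 | 60, 3.0 | 84, 4.2 |
| 3 | 10 | 50, 2.5 | 70, 3.5 |

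The first row is an upper figure for the planned between-arm comparisons, because the SAP does not say which times it will test.

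**Step 4: direction.** Sidedness is not stated, so two-sided tests are assumed. About half of the false positives would then favour the drug: 3.5 / 2 = 1.75 and 4.9 / 2 = 2.45. For insulin this needs an assumed direction of benefit, since the SAP states none.

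**Step 5: chance of at least one.** Independence gives 1 − 0.95^m for m tests, which is too high here because the variables are correlated and the sets overlap. A simulation with no drug effect used 4,000 replicates per scenario and 80 or 60 subjects. Correlations were assumed at 0.3–0.85 within an analyte and 0.1–0.5 between analytes, with each subset holding about half the subjects. The documents supply none of these values.

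| Family | Tests | At least one, if independent | At least one, simulated | At least three, simulated | Median count, simulated |
|---|---|---|---|---|---|
| 12 OGTT variables, entire cohort | 12 | 46% | 20–38% | – | – |
| 14 variables, five sets | 70 | 97.2% | 55–84% | 34–50% | 1–2 |
| 14 variables, seven sets | 98 | 99.3% | 65–91% | 43–64% | 2–4 |

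Simulated means stayed close to 3.5 and 4.9, as Step 3 requires. The medians are lower because false positives cluster: many trials show none or one, and some show many.

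**Not counted:** within-group tests, covariate-adjusted regressions, and any stratification of these endpoints by resting heart rate.

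**The case against.** The strongest reply is that the SAP never promises a single variable. It names a domain, says the domain rests on OGTT glucose and insulin data, and serves an objective framed as assessing measures in the plural. The study is a phase IV mechanistic trial, and neither document says a glycaemic claim will rest on any one p-value. The text also implies an order: the entire cohort comes first, the insulin and secretory-agent groups are introduced as further subsets, the indices are added as extras, and the duration split is only possible. That is fair. A reader should not infer that all sets have equal standing. An implied order of sets is still not a testing rule, and among the variables there is no order at all.

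It can also be said that several of these sets are not SAP inventions. Protocol 7.3 provides for stratification by post-prandial insulin response and for assessing effects by diabetes duration and baseline HbA1c. That stands, and a fix that dropped the insulin-response stratification without comment would conflict with the protocol. The 50 µU/ml cut-off at 60 minutes, however, appears only in the SAP.

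Finally, the documents do not rank glucose AUC above the other measures, and a fixed sequence or an adjusted threshold (0.05 / 12 = 0.0042 for the 12 OGTT variables) would also control error. True: the choice of variable is a judgement. The need to make some choice is not.

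**Conclusion.** The concern holds as a gap in a secondary family: a declared main glycaemic endpoint without a lead variable, a multiplicity rule or an exploratory label. The size is up to 70 between-arm tests with 3.5 false positives on average, or 98 and 4.9 with the optional strata. Without the fasting sample it is 3.0 or 4.2. These figures assume each planned comparison is run two-sided at the protocol's 0.05. Before any subset is opened, the chance of at least one false positive is about 20–38% under the assumed correlations, well above 5%.

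Three stronger readings are not supported:

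- That a null trial would typically show several significant results. The 3.5 and 4.9 are means; simulated medians are about 1–2 and 2–4.
- That a false positive is 97–99% certain. Those figures need independent tests, which these are not.
- That the sets were chosen after seeing results. The SAP is dated 14 December 2018, after the August 2018 finish that the protocol planned, but the documents do not say whether anyone had seen unblinded data.

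**What to change.** In the SAP, name the between-arm difference in change from baseline to week 24 in OGTT glucose AUC(0–120), in the entire cohort, as the single main glycaemic test at 0.05. This analysis is already planned and fits the SAP's stated interest in lowering post-prandial glucose. Week 24 follows the SAP; Protocol 9.6 sets the primary analysis at 12 weeks, which is a separate matter to reconcile.

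Keep the stratification by post-prandial insulin response from Protocol 7.3, either as a baseline stratification factor in that test or as a pre-specified supportive analysis, and state which. The SAP does not say at which visit the 60-minute insulin value is taken; for use as a factor it must be the baseline value.

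Report time-point levels, insulin AUC, Matsuda, HOMA-IR and the HbA1c, 60-minute-insulin, secretory-agent and duration subsets as estimates with 95% intervals, labelled exploratory.

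The cost is SAP wording; no new data are needed and no analysis is lost. The sponsor gives up significance claims from subsets and single time points. If data were already unblinded when the lead test is named, the report should disclose that.

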metformin alone or metformin plus an insulin secretion enhancer (sulfonylurea, DPP4 Inhibitors, or GLP-1 analogs) for at least 60 days prior to randomization. Following a 2 week lead-in period, subjects will be randomized in a 1:1 ratio to receive UDT (usual diabetes therapy) plus bromocriptine-QR or UDT plus placebo. Subjects must have a documented C-peptide level of >2 ng/ml from the screening visit. The circadian timing of the interventional therapy will be within 2 hours of waking in the morning. Following randomization subjects will be titrated to the maximum tolerated dose of the study drug over a four-week period. During these first 4 weeks, the daily dose of the study drug will be titrated up by one tablet (0.8 mg bromocriptine-QR or 1 matching placebo tablet) per day on a weekly basis until a maximal tolerated dose of at least two tablets (1.6 mg/day bromocriptine-QR or 2 placebo tablets) and no more than four tablets (3.2 mg/per day b-QR or 4 placebo tablets) is achieved. During the first 4 weeks of the study, subjects will be called weekly to monitor for possible adverse events. Subjects will be maintained at their maximum tolerated dose of between two to four tablets per day (1.6 to 3.2 mg bromocriptine-QR per day or 2 to 4 placebo tablets) for the duration of the study. Subjects unable to tolerate two tablets per day of study drug will be terminated from the study and any further analyses. Subjects will be seen at 4 weeks after randomization, at 12 weeks after randomization, and then at study end (week 24 or early termination). A primary analysis of the primary and secondary endpoints will be performed after 12 weeks with a secondary analysis conducted on these study endpoints at 24 weeks. Subjects will be contacted 30 days after stopping the study drug to record any adverse events that occurred after cessation. During the study period subjects will be advised to perform home blood glucose monitoring at least on a daily basis. Subjects will be required to continue their usual anti-diabetes regimen during the study but will be allowed to alter the dosages of these medications and/or add or subtract medications as deemed necessary by the Principal Investigator to optimize blood glucose control to avoid hypoglycemia or persistent hyperglycemia. In any case, rescue therapy for hyperglycemia will be administered if a subject has two consecutive fasting glucose measurements >270 mg/dL spaced  $\leq 7$  days apart before week 12, or two consecutive fasting glucose measurements >250 mg/dL spaced  $\leq 7$  days apart or a HbA1c >11% at or after week 12. The choice of rescue therapy will be at the discretion of the Principal Investigator and may include adjustments in the dosages of the medications that the subject is already on and/or addition of other glucose lowering therapies. The subjects with concurrent antidiabetes medication changes may remain "on study" for the remainder of the study until week 24 undergoing all evaluations if in the opinion of the investigator this does not pose any serious risk to the subject or the study objectives unless the rescue therapy requires insulin, in which case the subject will be withdrawn from the study as per the exclusion criteria for the study. Subjects will receive a complete physical and neurological exam and clinical laboratory assessments at baseline and at the completion of the study. The primary and secondary endpoints will be evaluated at baseline, week 4, week 12, and week 24 or at early termination. Subjects will be evaluated using the procedures listed below.

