#### **7.2.2.7 Visit 3 (Visit 1plus 12weeks [ $\pm$ 3 days])**

Subjects will be instructed to arrive having fasted from the night before this visit and having taken their morning dose of the study drug with time taken noted.

- Assessment for any AE/SAE will be completed
- Medical history will be taken
- Sudorimetry
  - Sudoscan
- Autonomic Function Tests
  - Heart Rate Variability (HRV)
- Blood will be taken for the determination of HbA1c, lipids, c-peptide, neuroendocrine factors, inflammatory markers and oxidative/nitrosative stress (see study schedule).
- Total amount of blood drawn at this visit will be approximately 55-60 ml.
- Urine will be obtained for measurement of microalbumin
- An OGTT will be administered and OGTT glucose and insulin levels will be obtained at 0, 30, 60, 90 and 120 minutes post-glucose challenge.
- Skin Blood Flow (SkBF)
  - Continuous Laser Doppler
- Quantitative Sensory Tests (QST)

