#### **Subject withdrawal due to deterioration of glycemic control**

If a subject has a HbA1c of > 12% or fasting glucose readings of greater than 275 mg/dl on two consecutive days, then the subject's regimen must be adjusted to include medications offering stricter glycemic control. As per the exclusion criteria, subjects requiring insulin must be withdrawn from the study. If the subject's HbA1c remains > 12%, he/she should cease study treatment to be stabilized on alternative medications. Subjects that are withdrawn will be referred to their primary care physician or endocrinologist for further diabetes medication adjustments as needed.

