#### **Replacement of subjects**

Subjects that are withdrawn within 4 weeks following completion of study drug titration will be replaced. As far as possible, for subjects who are withdrawn from the study, all safety examinations scheduled for the final study day will be performed prior to withdrawal.

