## 9.6 ANALYSIS POPULATIONS

The primary analysis of the study will be the assessment of the primary and secondary study endpoints after 12 weeks of study drug treatment. The secondary analysis of the study will be the assessment of the primary and secondary study endpoints after 24 weeks of study drug treatment.

Dropouts will be replaced as described in section 9.1.

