Between treatment group differences in the change from baseline to week 24 in the levels of the above factors will be analyzed in the overall cohort as well as with stratification by baseline RHR ($< \geq 70$ BPM) as described above for the analysis of autonomic function markers as well as stratification by baseline HbA1c ($< \geq 7.0$) as described above for the analysis of glycemic control parameters.

Statistical Methods:

Between treatment group (bromocriptine-QR vs. placebo) differences in change from baseline to week 24 and within group changes from baseline to week 24 of all primary and secondary endpoints will be analyzed using Independent Samples T-tests. If the data are not normally distributed in raw form or in some cases after simple log transformation, then appropriate non-parametric tests will be used instead. Within group analyses will be performed using paired samples T-test or repeated measures ANOVA as appropriate. The treatment effects on the primary and secondary outcomes will also be assessed after adjustment as needed for other potential factors that could influence the specific endpoint being analyzed such as duration of diabetes, baseline HbA1c, baseline RHR and/or change in RHR from baseline, concomitant medications and other baseline demographics as appropriate using categorical stratified analyses as discussed above and/or multivariable regression analyses methods.

References:

4. Egan BM: Insulin resistance and the sympathetic nervous system. *Curr Hypertens Rep* 2003;5:247-254

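### The co-secondary glycaemic comparison is confined to week-24 completers and uses an unadjusted change-score t-test, so it can be biased in either direction and is less precise than the scheduled data allow

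*SAP*

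**What the plan says.** **Analysis set.** For OGTT glucose and insulin, the Matsuda index and HOMA-IR, the SAP (Secondary Endpoints, item 1) states: "All subjects completing 24-weeks of study drug treatment with data for baseline and week 24 OGTT will be included in the analyses". The natural reading is completers only.

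**Test.** Under Statistical Methods in the SAP, arm differences in change from baseline to week 24 "of all primary and secondary endpoints will be analyzed using Independent Samples T-tests". Repeated-measures ANOVA is mentioned only for within-group analyses. Covariate adjustment is allowed as needed, and the baseline value of the outcome is not named. No missing-data method is given for these endpoints.

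**Exits.** Protocol 3.1: "Subjects unable to tolerate two tablets per day of study drug will be terminated from the study and any further analyses". Protocol 9.1, on loss of glycaemic control: "subjects requiring insulin must be withdrawn from the study". Protocol 9.1, on replacement: "Subjects that are withdrawn within 4 weeks following completion of study drug titration will be replaced".

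**Data scheduled.** At week 12 (protocol 7.2.2.7) "An OGTT will be administered and OGTT glucose and insulin levels will be obtained", as at baseline and at week 24 or early termination. Fasting glucose and insulin for HOMA-IR are also taken at week 4 (7.2.2.5). Protocol 9.6 gives week 12 priority: "The primary analysis of the study will be the assessment of the primary and secondary study endpoints after 12 weeks of study drug treatment". The SAP's OGTT analysis uses baseline and week 24 only.

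**The concern.** Randomisation protects a comparison of everyone randomised. It does not protect a comparison of those who stayed, if staying depends on arm and on glycaemia. Here the protocol's own rules create both links.

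- **Insulin withdrawal** removes poorly controlled subjects. If the drug works, these are more often on placebo, so the placebo completers look better than their arm and the difference shrinks.
- **Intolerance** removes subjects mainly on active drug. If intolerance is related to baseline glycaemia, the active completers differ from their arm, in a direction nobody can state beforehand.

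Replacing early withdrawals restores the head count but not the randomised comparison. Without counts by arm, a reader of the results could not judge either route. The stake is co-secondary objective 1. The primary autonomic endpoints are not covered by this completer sentence.

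**Working it through.** **The plan's own figure.** Protocol 9.7 gives power above 0.80 with 80 subjects for a 10% change, with no SD and no dropout allowance, so it cannot be reproduced. Solving backwards (two-sided 0.05, 40 per arm), the SD of the percent change must be at most 10 × √20 / (1.960 + 0.842) = 15.96. This says nothing specific about the glycaemic endpoints.

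**Precision, no dropout.** Work in units of the outcome SD, with n = 40 per arm (protocol 9.7) and ρ the baseline to week-24 correlation (assumed).

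- SE of the change-score t-test = √(4(1−ρ)/n)
- SE with baseline adjustment = √(2(1−ρ²)/n)
- Ratio, adjusted to unadjusted = √((1+ρ)/2)

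At ρ = 0.5: 0.224 against 0.194, ratio 0.866, so adjustment cuts the SE by 13%. At ρ = 0.8: 0.141 against 0.134, ratio 0.949, a cut of 5%. Put the other way round, the unadjusted SE is 15% or 5% larger than it need be.

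Week 12 adds little precision. At 20% random dropout, simulated SEs were 0.223 to 0.246 (completer t-test), 0.202 to 0.213 (completers, baseline-adjusted) and 0.199 to 0.207 (baseline plus week 12).

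**Bias.** Assumed: true difference −0.50 SD at weeks 12 and 24; correlations 0.5 (baseline with later visits) and 0.7 (week 12 with week 24). Write h(c) = φ(c)/Φ(c).

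*Insulin withdrawal set by the week-12 level.* Everyone above c leaves, with c chosen so that a given share of placebo is lost. Completer difference = −0.50 + (0.7 − 0.5) × [h(c) − h(c + 0.5)].

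- 10% of placebo lost: c = 1.282; −0.50 + 0.2 × (0.195 − 0.085) = −0.478.
- 20% lost: c = 0.842; −0.50 + 0.2 × (0.350 − 0.178) = −0.466.

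*Withdrawal set by the week-24 level.* The multiplier becomes 1 − 0.5 = 0.5, giving −0.445 (10%) and −0.414 (20%).

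*Intolerance.* 15% of the active arm leaves, with correlation r between the tendency to intolerance and baseline glycaemia. h(1.036) = 0.274, so the shift is r × 0.274 × (1 − ρ). At r = ±0.3 and ρ = 0.5 it is ±0.041, giving −0.459 or −0.541. At ρ = 0.8 it is ±0.016. At r = 0 it is nil.

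Simulation agrees with these closed forms to within about 0.005 and adds the baseline-adjusted model with week 12:

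| Scenario | Completer t-test | Model, all randomised |
|---|---|---|
| No dropout | −0.50 | −0.50 |
| Week-12 level, 10% / 20% | −0.476 / −0.465 | −0.499 / −0.500 |
| Week-24 level, 10% / 20% | −0.447 / −0.415 | −0.440 / −0.399 |
| Intolerance, r = +0.3 / −0.3 | −0.455 / −0.543 | −0.498 / −0.500 |
| Intolerance (+0.3) with 10% week-12 level | −0.440 | −0.503 |

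Baseline adjustment in completers alone does not cure the week-12 route: it gives −0.446 (10%) and −0.416 (20%).

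**Stronger dropout.** Let exit depend on the change at week 12, with baseline to week-12 correlation 0.6. If placebo loses worsening subjects (30% against 10%), the completer bias is 0.137 to 0.210 SD toward the null, with SE 0.221 to 0.252, or 0.62 to 0.83 SE. If the drug arm loses poor responders (23% against 10%), it is 0.110 to 0.159 SD away from the null, with SE 0.219 to 0.242, or 0.50 to 0.66 SE. The model's bias was at most 0.005 SD.

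**The case against.** Four points on the other side carry weight.

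- **The size is not established.** This stands. Withdrawal rates, SDs and correlations are all assumed. The intolerance bias disappears if intolerance is unrelated to baseline glycaemia, and if all visits are equally correlated, withdrawal on the week-12 level gives about zero bias. A reader might infer that the completer result is known to be wrong by some percentage, or that it favours the drug. The documents support neither.
- **The model may not repair the insulin route.** This also stands. Withdrawal is triggered by fasting glucose or HbA1c during follow-up, possibly after the last OGTT. If it follows the unseen week-24 level, the model is no better than the completer test (table above). Subjects who leave in titration contribute little beyond baseline.
- **The SAP already permits regression.** Only in part: adjustment is optional, and within completers it can increase the insulin-route bias. A reader might also blame the precision loss on leaving out week 12. That is not so: nearly all of the loss comes from not adjusting for baseline. Week 12 mainly helps with bias.
- **A completer comparison is a recognised choice for a mechanism study.** True, which is why it should be kept as supportive.

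A reader might take the wording in protocol 3.1 on intolerant subjects as an order to delete their data, needing a protocol amendment. The word analyses there can equally mean assessments, as it does in the Study Design part of the protocol outline. The SAP, dated 14 December 2018, also comes after the planned last visit in August 2018. A SAP sentence is enough.

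**Conclusion.** The point holds, at the level of a change worth making. The SAP's glycaemic comparison rests on a group selected after randomisation by rules tied to arm and outcome, and it leaves scheduled data out of the comparison of arms. Bias in either direction is possible; its size cannot be set from the documents and is probably below one SE (0.83 SE at most in the scenarios examined, all on assumed rates and correlations with a true effect of 0.5 SD).

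The precision loss is firmer, because it needs no dropout: adjustment cuts the SE by 5% to 13% for ρ from 0.8 to 0.5. It still rests on an assumed ρ.

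**What to change.** Change the SAP only.

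1. Define the analysis set for OGTT AUC, Matsuda and HOMA-IR as all randomised subjects, including those withdrawn for intolerance or insulin and those later replaced, with all values collected up to exit.
2. Make the main analysis a baseline-adjusted repeated-measures model using the baseline, week-12 and week-24 values, plus week 4 for HOMA-IR, on the log scale where skewed. State a visit window for early-termination OGTTs, so that they count only near week 12 or week 24.
3. Keep the completer t-test as supportive.
4. Report by arm the counts of intolerance, insulin withdrawal and background glucose-lowering drug changes, which protocol 3.1 permits.

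**Cost.** Some SAP text and modest programming. No new visit or test is needed: the measurements are scheduled, and concomitant treatments (6.2) and withdrawal reasons (9.1) are already recorded. The model brings a missing-at-random assumption, which the report should state with its limits. Leave the care and withdrawal rules as they are.
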